### ***Adverse Experiences Associated with Self-Report***

The trials will involve the use of assessments that could reveal sensitive information (e.g., mood disturbance, substance use). The instruments are not used to communicate psychiatric diagnosis to the participant and procedures are in place to protect participant confidentiality. Possible resolutions for this type of adverse experience include referring participants to their primary care physicians, and/or other physicians, and/or other mental health providers. Other procedures to minimize this type of adverse experience are described in the section K above.

### ***Adverse Experiences Associated with the Nicotine Patch***

Adverse experiences associated with the nicotine patch are almost always of a mild nature. Potential risks arising from use of nicotine patch therapy are mostly limited to nausea, erythema, and other dermatologic reactions. Procedures to minimize this type of adverse experience are described in the section K above. The incidence of side effects with the patch is small and can be locally treated or reversed with discontinuation of the patch. The risk of nicotine toxicity is extremely low. Appropriate warnings about not smoking while using the patch will be issued each time patches are dispensed. Management of AE's are done in accordance with standards of clinical practice and almost always are relieved by a reduction in dose, or although rarely necessary, discontinuation of patch use.

#### ***Adverse Experiences Associated with Nicotine Abstinence/Withdrawal***

Participants may also experience nicotine abstinence/withdrawal effects. These effects may include irritability, difficulty concentrating, insomnia, anxiety, dysphoria, and increased hunger. None of these effects results in serious adverse events.

#### ***COVID-19 Risk Mitigation Plan***

The below actions will be implemented to mitigate the risk of COVID-19 transmission and acquisition:

- In general, the Lao research team and US investigators in Lao PDR will follow COVID-19 prevention plan/guidance of the Ministry of Health of Lao PDR.
- Body temperature check: Before in-person interviews, body temperature of research staff and participants will be measured using a portable non-contact infrared digital thermometer. Research staff's body temperature will be measured once per day before the first interview. Persons with a temperature >38.5°C will not be allowed to participate in the interviews and will be advised to seek further health care.
- Masking: All research staff and participants will be provided surgical-style masks and will be required to wear masks during in-person interviews.
- Hand washing: Research staff and participants will be asked to wash their hands before and after the interviews.
- Wearing gloves: Research staff will be required to wear gloves when direct physical contact with research participants is needed, discard gloves after contact appropriately, and wash hands.
- Social distancing: Research staff and participants will be required to maintain social distancing of 6-feet (2 meters) in all directions unless necessary to conduct intervention or measures.
- Disinfection: Research areas and tools, including rooms, tables, chairs, and tablets will be appropriately disinfected as recommended by the Ministry of Health of Lao PDR. Disinfecting will take place before the first participant, between participants, and after the last participant. Inexpensive supplies such as pens, small notebooks, or participants' folders will be given to participants without reuse/recycling.
- The Directors of the participating hospitals and of the NCLE (i.e., site PI) will be informed if the research staff becomes aware of a team member or a participant who tests positive for COVID-19.
- As the nature of COVID-19 remains dynamic, the NCLE will regularly evaluate this COVID-19 prevention plan and revise the plan if necessary.

## **O. DATA SHARING**

The US and Lao investigators have equal rights to access to study data.

All qualitative data will be deidentified during the verbatim transcribing process and translation to English. Deidentified data will be transferred to the PI in encrypted files.

Quantitative data collected by REDCap program will be transmitted between the REDCap app and the OUHSC secure REDCap server on a daily basis using a secure, encrypted transmission (SSL/HTTPS). REDCap has been used by several institutions in Lao. The tablets with REDCap mobile app are password protected, encrypted, and can be remotely wiped if lost.

Quantitative data collected by our Insight app on smartphones will be automatically encrypted and will be automatically sent to our OUHSC mHealth Shared Resource secure servers whenever there is active internet (4G) connection. The web browser application linking the investigator's computer to the database uses HTTPS protocol (SSL certificate with encryption), which will guarantee the protection of data transferred from the web browser to the backend database. The backend database is hosted by the OUHSC mHealth Shared Resource in a secure setup.

Data storage, or data transfer if there is a request, will follow all OUHSC's requirements for data security. In all components of the research project, participants will be assigned unique identification numbers, and this identification numbers will be used in all data transfer and data analysis. When data sharing is requested, de-identified data files will be transferred on a password-protected and encrypted drive and will be maintained on institutional servers with appropriate antivirus software. Final de-identified data files will be maintained by the PI at OUHSC, and all other copies of data files will be deleted after the publication of outcome papers.

## P. CONFIDENTIALITY

**Protection against Confidentiality Breach:** Confidentiality will be maintained for all data and contact information. To protect against the risk of a confidentiality breach, the following steps will be taken:

- REDCap will be used to collect and manage information for most procedures, including screening eligible participants, administering in-clinic assessments at baseline and follow-ups, and capturing participants' information from medical records. REDCap is a secure web-based application designed to comply with all HIPAA regulations. Data will be collected by participants (e.g., self-interviews for baseline assessment) or by research staff (e.g., screening or reviewing medical records) on tablets using the REDCap Mobile App. Each participant will be given a unique identification number (UIN) in this study, and the UIN will be used in all data collection procedures that are managed by REDCap. The REDCap Mobile App employs encryption at-rest on the mobile device's hard drive so that all important data and information stored on the device are properly protected from unauthorized or malicious users. All data are transmitted between the app and the OUHSC secure REDCap server using a secure, encrypted transmission (SSL/HTTPS). REDCap has been used by several institutions in Lao. The tablets are password protected, encrypted, and can be remotely wiped if lost.
- All data related to participants will be identified only by the UIN. A master list of participant UINs linked to participant names will be stored in locked file cabinets in locked study offices at SH or CH. Access to the master list will be limited to those with privileges. After completion of the study and data analysis, the identification file will be destroyed.

- Participants will not be identified in any public reports or documents. In qualitative component reports, if any, only participant initials or random initials will be used for quotations. In the trials, only aggregate data will be reported and released. At no time will individual names appear in any report, article, or manuscript related to the study.
- To minimize risks related to participant information potentially being disclosed via the use of smartphones, the following features are designed to ensure the security of the assessment data:
  - o The data stored on the smartphone device is in a SQLite database in a sandbox environment, where read/write operations are only available through the programming application (i.e., no file or output is readable to end users).
  - o A 10-character password (only known to researchers) is required to authenticate the current user before data can be manually accessed on the smartphone.
  - o Encrypted smartphone data will be automatically sent to our OUHSC mHealth Shared Resource secure servers multiple times per day.
  - o The web browser application linking the investigator's computer to the database uses HTTPS protocol (SSL certificate with encryption), which will guarantee the protection of data transferred from the web browser to the backend database.
  - o The backend database is hosted by the OUHSC mHealth Shared Resource in a secure setup.
  - o Software will be downloaded onto each study phone so that phones can be remotely wiped if lost.
- During the consent process, participants will be informed of the potential for psychological distress or discomfort associated with unintentional disclosure of personal information to non-study staff, and the nature of the questions to be asked will be made clear.
- Participants will be informed of the safeguards in place and encouraged to contact investigators at any time to discuss any confidentiality concerns that arise.

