**Table. Trial Assessments**

Variable type	Measure	BL	W*	12
Descriptors/ potential moderators	Demographics; Health Literacy 	X		X #
	Alcohol and Drug Use 	X		X
	COVID-19–related issues,  co-morbidities 	X		X
	Dependence – Heaviness of Smoking Index 	X		
Feasibility/ Adherence to AT app	Numbers of messages/images/videos opened and completed; weekly assessments opened and completed; activity logs	Date/time stamps in Insight		
Phase-Based Model mechanisms	Wisconsin Smoking Withdrawal Scale 	X		X
	Reasons for Quitting (Intrinsic, Extrinsic) 	X		X
	Contemplation Ladder 	X	X	X
	Kessler Psychological Distress Scale (K10) 	X	X #	X
	Positive and Negative Affect Schedule 	X	X #	X
	Self-Efficacy (related to smoking cessation) 	X	X #	X
Cancer survivorship	Fear of cancer recurrence (survivors only),  family support,  and spiritual well-being 	X		X
Qualitative, open-ended assessment	An in-app participant-initiated assessment—“Share with us anything on your mind”—with an open text field to capture the participant’s thoughts, feelings, and behaviors	Initiated anytime by participant		
Primary outcome	Smoking status in the past week 	X	X #	X
	Expired carbon monoxide at follow-up 	X	X	X
Secondary outcomes	E.g., number of quit attempts, days abstinent, and other tobacco product use 	X		X

Abbreviations: AT, automated treatment; BL, baseline; W, weekly; 12, 12-week follow-up. \**Delivered via Insight app*; \*\**Brief versions of the scales*.

preliminary nature of the RCT, we do not expect to have sufficient power for full hypothesis testing. However, from our previous work, we anticipate that the abstinence at the 12-week follow-up will be 8% in the SC group. With 40 participants in each group, we will have 80% power to detect a difference as small as 20% in smoking abstinence rates between groups ( $\alpha=0.05$ , one-tailed, unadjusted).

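### The protocol lets quotations in reports carry a participant's true initials, which conflicts with its UIN-only rule and its statement that qualitative data are de-identified

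*Combined protocol and SAP*

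**What the plan says.** Sections K2 (Protection against Risks) and P (Confidentiality) contain the same set of confidentiality bullets. On quotations, both say: "In qualitative component reports, if any, only participant initials or random initials will be used for quotations". The two kinds of initials are alternatives, and nothing says who chooses between them or on what basis.

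Three other statements bear on this:

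- In K2 and P, on the identifier attached to data: "All data related to participants will be identified only by the UIN".
- In K2 and P, on publications: "Participants will not be identified in any public reports or documents". The same bullet adds that individual names will not appear in any report.
- In Section O (Data Sharing), on interview and free-text material: "All qualitative data will be deidentified during the verbatim transcribing process and translation to English". The next sentence there reads: "Deidentified data will be transferred to the PI in encrypted files".

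For the secondary point, the Table of Trial Assessments includes "An in-app participant-initiated assessment" "with an open text field to capture" the participant's thoughts, feelings and behaviors, which the participant may start at any time. K2 and P say of the phones: "Encrypted smartphone data will be automatically sent to our OUHSC mHealth Shared Resource secure servers multiple times per day". Section O also describes automatic transfer from the phones, but words it for quantitative data only.

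**The concern.** True initials come from the name. Under the quotation rule, staff who print them beside a quotation are complying with the protocol, although the rest of the plan is written so that nothing derived from the name travels with the data.

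What is at stake is participant protection. Section K1 names breach of confidentiality first among the risks. The quotations will concern smoking, quitting and the obstacles to it, in cancer survivors and caregivers. The trial enrols 80 people, 40 survivors and 40 caregivers, at Setthathirath Hospital and the Lao National Cancer Center. Caregivers are found by asking non-smoking patients whether they have a caregiver who smokes (Stage 2 and Section J), so some people outside the trial may know who was approached. In that setting a true initial gives a reader a clue to the speaker that a random label does not. K2 and P destroy the file linking names to UINs after analysis, but initials in a published report cannot be withdrawn.

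**Working it through.** The plan states no figure on this point and no arithmetic applies. The check sets the statements side by side.

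**Step 1: what the quotation rule permits.** The sentence in K2 and P restricts labels to two kinds and leaves both open. True initials are therefore permitted, though not required.

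**Step 2: compare with the UIN-only rule (K2, P).** This rule makes the UIN the sole identifier on participant data. Section O repeats the idea by requiring identification numbers in all data transfer and analysis. If both are followed, the files from which quotations are drawn contain no initials. Printing true initials then requires that a name-derived element was kept with the text, or that it was recovered later from a source holding names. The protocol does not say which. Neither route fits a rule under which the UIN is the only identifier.

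**Step 3: compare with Section O.** Qualitative data are said to be de-identified while they are transcribed and translated, and the PI receives the de-identified version. A quotation from that version has no true initials to print unless they survived the de-identification step or were added back afterwards.

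**Step 4: compare with the promise about public reports (K2, P).** The promise is that nobody is identified and no names appear. Initials are not names, and the documents do not show that initials would identify a given participant. This promise is put under avoidable strain but is not shown to be broken.

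**Step 5: is the option needed?** Random initials, the other alternative in the same sentence, already let a reader follow one speaker across quotations. Nothing in the mixed-methods plan (Stage 2 and Section M) depends on true initials.

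**Step 6: the open-text route.** Typed text in the app has no obvious transcription stage. K2 and P send smartphone data to the OUHSC servers without restricting the statement to quantitative data. Section O restricts its statement to quantitative data and gives no route for the open-text field. The sections are therefore incomplete when read together. They do not state that unscreened text is uploaded.

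**The case against.** The strongest defence is that the UIN rule governs stored data while the initials sentence governs reports, so the two need not meet. The sentence is itself meant as a protection: it applies to reports that may never be written, it excludes names, and its second option is safe. Investigators could comply with every section by choosing random initials. Much of this stands. It shows that no breach is inevitable and that the remedy is a small change of wording. It does not remove the conflict, because using the first option still needs a name-derived element that the data rules and the de-identification step are meant to exclude.

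A reader might also infer stronger claims that the documents do not support:

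- **That free text reaches OUHSC before it is de-identified, breaking the promise in Section O.** For REDCap, Section O words the daily transfer for quantitative data, and the capture method for the 3-month open-ended questions is not stated; transcription before any transfer is possible. For the app field, early upload is a plausible reading of K2 and P but is not stated. In either case, Section O promises de-identified files to the PI. Arrival on a secure OUHSC server, with encrypted transfer and UIN coding, is not that transfer. K2, O and P do mention a browser link from the investigator's computer to the database. That is a reason to clarify the route, not evidence of a breach.
- **That small subgroups would make initials unique.** The protocol says the 3-month questions differ by abstinence status. No section says quotations will be labelled by survivor or caregiver status, or by sex, so cell sizes built on those labels have no basis in the plan. Nor can a count of abstainers be taken from the power statement: 8% is the anticipated standard-care rate, but the 20% is a detectable difference, not an expected result. Uniqueness within a group would in any case not be the same as identification.

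**Conclusion.** The point holds as an internal conflict. K2 and P permit a name-derived label on quotations, while the same sections make the UIN the only identifier and Section O says all qualitative data are de-identified. The consequence is an avoidable recognition risk among 80 participants from two hospitals in one city. The documents do not allow that risk to be quantified. The finding rests on the plain reading that the first option means a participant's real initials, since random initials are named separately. It does not depend on any assumption about how quotations will be grouped.

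The size is modest: one phrase, occurring in two sections, with no bearing on the primary outcome, its analysis or the sample size. It still merits correction before any quotation is published.

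The open-text matter is secondary and is not an error. Section O is silent on the route for the in-app field while K2 and P are worded broadly, and the three should be made to agree.

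**What to change.** In Sections K2 and P, strike the participant's own initials from the sentence on quotations, so that only random labels derived from neither the name nor the UIN may be used. This has no cost: random initials are already allowed, and no analysis changes.

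As a wording clarification, add a sentence to Section O giving the route for the in-app open-text field and the point at which it is de-identified, and align the smartphone transfer statements in K2 and P with it. The cost is the protocol wording.
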